8.2.2 ADA and safety

Adverse events and SAEs during the study (separately for on-treatment and on-study periods) will be summarized by ADA status (treatment-emergent ADA positive, ADA negative), if enough data are available. The on-treatment and on-study periods are as defined in Section

3.5.1. AEs and SAEs will also be evaluated by causality as assessed by the Investigator. The potential impact of ADA on hypersensitivity will also be assessed.

8.2.3 ADA and eosinophil levels

Eosinophil levels will be summarized by visit for the following ADA response categories of participants: treatment-emergent ADA positive, ADA negative, ADA persistently positive, and ADA positive with titre > median of maximum titre, if enough data are available. A line plot of eosinophil levels by visit and ADA status will also be presented.

8.2.4 ADA and PK

Benralizumab serum concentrations will be summarized by visit and ADA status (treatment emergent ADA positive, ADA negative, ADA persistently positive, ADA positive with titre > median of maximum titre) for participants in the PK analysis set, if enough data are available.

8.3 Partial dates for adverse events and prior/concomitant medications

Dates missing the day, or both the day and month of the year will adhere to the following conventions to classify TEAEs and to classify prior/concomitant medications:

The missing start day will be set to:

First day of the month of occurrence, if the start YYYY-MM is after the YYYY-MM of first study treatment

The day of the first study treatment, if the start YYYY-MM is the same as YYYY-MM of the first study treatment

The date of informed consent, if the onset YYYY-MM is before the YYYY-MM of the first study treatment.

The missing end day will be set to:

The last day of the month of the occurrence, if the end YYYY-MM is after the YYYY-MM of the first study treatment.

Death date if the participant died in the same month.

The day of last study treatment if the YYYY-MM of occurrence is the same as the last study treatment.

If the start date is missing both the day and month, the start date will be set to:

The date of the first study treatment, if the start year is the same as the year of the first study treatment

January 1 of the year of occurrence.

If the end date is missing both the day and month, the date will be set to:

Last study treatment date if the year of occurrence is the same as the last study treatment date.

Date of death if the participant died in the same year.

December 31 of the year of occurrence.

If the start date is null, the date will be set to:

January 1 of the same year as the end date, if the end date suggests that the start date could be prior to the date of first study treatment.

The date of first study treatment.

If the end date is null and not recorded as ongoing, the date will be set to:

The date of the first study treatment, if the start date is prior to the date of first study treatment.

The date of last visit, if the start date is on or after the date of first study treatment.

If the end date is null and recorded as ongoing, the end date will not be imputed.

Statistical Analysis Plan
D325AC00002 – 2.0

AstraZeneca
11/02/2021

SIGNATURE PAGE – WET INK

Protocol	D325AC00002
Document Name	Statistical Analysis Plan
Document Version	2.0
Document Date	11 February 2021

PPD

PPD

PPD

Signature Page – Wet Ink

Study

PPD

Biostatistician:

Principal Biostatistician

PPD

PPD

Signature Page – Wet Ink

Approved by:

PPD

AstraZeneca

PPD

Signature

Date

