3.5.1 Adverse Events

All AEs will be collected starting from screening (Visit 1), throughout the treatment period, and including the follow-up period.

Serious AEs will be recorded from the time the participant signs the informed consent form (ICF), throughout the duration of the study.

Any non-serious AEs with a start date later than 12 weeks after the last dose of IP will be excluded from the analysis.

Adverse events will be coded using the most recent version of the Medical Dictionary for Regulatory Activities (MedDRA) that will have been released for execution at AstraZeneca/designee per the Data Management Plan.

A per Section 9.4.3.2 of CSP, the following events are considered treatment emergent:

AEs with an onset date on or after the first dose of IP

Worsening of pre-existing events on or after first dose of IP

For the analysis, an AE will be defined as Treatment Emergent AE (TEAE) if it has an onset date on or after the first dose of IP. Applying this definition, also the worsening of pre-existing events on or after the first dose of IP will be included in the analysis as Investigators are instructed to record these as new events.

The handling of partial/missing dates for AEs is detailed in Appendix 8.3. Treatment Emergent AEs data will be categorized according to their onset date into the following study periods:

AEs in the pre-treatment period are defined as those with an onset prior to the day of first dose of study treatment.

AEs in the on-treatment period are defined as those with onset date between day of first dose of study treatment and the day of the scheduled follow-up visit or date of last dose + 12 weeks, whichever is earlier. If the upper limit is after the end of on-study period, then the upper limit is set to the end of on-study period.

AEs in the post-treatment period are defined as those with onset date after the on-treatment period defined above.

AEs in the on-study period are defined as those with onset on or after the day of first dose of study treatment.

If an AE has a missing onset date then unless the stop date of the AE indicates otherwise, this will be considered an on-treatment AE. Similarly, if an AE has a partial onset date, then unless the partial onset date or the stop date indicates otherwise, this will be considered an on-treatment AE.

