AEs in the on-treatment double-blind period are defined as those with an onset date between day of first dose of study treatment and day prior to first dose of study treatment in OLE period. For participants who do not transition into OLE all the AEs in the on-treatment period are included in the on-treatment double-blind period.

AEs in the on-treatment OLE period are defined as those with an onset date between the day of first dose of study treatment in the OLE period and the day of the scheduled follow-up visit or date of last dose + 12 weeks, whichever is earlier. If the upper limit is after the end of on-study period, then the upper limit is set to the end of on-study period.

The Investigator will assess the causal relationship between IP and each AE, and answer ‘yes’ or ‘no’ to the question ‘Do you consider that there is a reasonable possibility that the event may have been caused by the investigational product?’. For SAEs, the causal relationship will also be assessed for other medication and study procedures. Note that for SAEs that could be associated with any study procedure, the causal relationship is implied as ‘yes’.

Adverse events that have missing causality (after data querying) will be assumed to be related to study drug.

The Investigator will assess the severity of each AE as “Mild”, “Moderate” or “Severe”. Adverse events that have missing severity will be assumed to be severe.

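### The partial-date rule has no anchor at the first open-label dose, so an AE with a missing start day in that calendar month is classed as double-blind, and under placebo for participants who switch

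*SAP*

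**What the plan says.** SAP Appendix 8.3 says that incomplete dates "will adhere to the following conventions to classify TEAEs and to classify prior/concomitant medications". For a missing start day it compares the start month with one dosing date only, the first study treatment:

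- Same month: "The day of the first study treatment, if the start YYYY-MM is the same as YYYY-MM of the first study treatment".
- Later month: "First day of the month of occurrence, if the start YYYY-MM is after the YYYY-MM of first study treatment".
- Earlier month: the consent date.

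For a missing day and month, it uses "The date of the first study treatment, if the start year is the same as the year of the first study treatment", and otherwise 1 January. No start-date rule mentions the first OLE dose, although the SAP names that date separately in 3.1.2 and 3.5.1.

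SAP 3.5.1 then allocates events by period: "Treatment Emergent AEs data will be categorized according to their onset date into the following study periods". A double-blind AE is one with "an onset date between day of first dose of study treatment and day prior to first dose of study treatment in OLE period", and the OLE period begins on the day of that dose. For a partial onset date, 3.5.1 adds that "unless the partial onset date or the stop date indicates otherwise, this will be considered an on-treatment AE". SAP 4.2.9 and 4.2.9.1 report AEs by period and by treatment group.

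**The concern.** The period split depends on the imputed onset date, but the imputation takes no account of the date at which the periods divide. Every participant who enters the OLE receives benralizumab (SAP 1.2.3). For a participant randomised to placebo, the first OLE dose is the first exposure to active drug. An AE from that calendar month with no start day defaults to the placebo column of the randomised safety comparison and leaves the OLE tables. Hypersensitivity is an identified risk (Protocol 2.3), and it and injection site reactions have their own summaries (SAP 4.2.9.1), so the first weeks on active drug are of interest.

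The SAP does not allow partial start dates for OCS or restricted medications (3.1.5.1, 3.2). It provides for them for AEs, so such cases are foreseen.

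**Working it through.** The plan gives no figure on this point, so the rules were applied as written.

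**Inputs from the documents**
- The double-blind period is 36 weeks = 252 days (SAP 1.2.2). The Visit 13 window is ±3 days (Protocol Table 2).
- The period boundary is the day of the first OLE dose (SAP 3.1.2, 3.5.1).
- The start-day rule is that of SAP Appendix 8.3.

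**Assumptions**
- The start day is missing, the true onset is uniform over the days considered, and the stop date does not constrain the start.

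**Step 1: which rule applies.** 252 days exceeds any calendar month, so the first OLE dose always falls in a later month than the first dose. The missing day is therefore set to the 1st.

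**Step 2: one case.** First dose (placebo) is 5 Jan 2022. Adding 252 days puts the first OLE dose on 14 Sep 2022. True AE onset is 19 Sep 2022, day not recorded. The imputed onset is 1 Sep 2022, before 14 Sep, so the AE is double-blind and under placebo.

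**Step 3: share misplaced in that month.** Take a 30-day month with AE day *a* and dose day *d* each from 1 to 30, giving 900 pairs. The error occurs when *a* ≥ *d* and *d* ≥ 2. The count is the sum of (31 − *d*) for *d* = 2 to 30, or 29 + 28 + … + 1 = 435. The share is 435/900 = 48.3%. No pair is misplaced the other way.

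**Step 4: real calendar.** The rule was run over 1,460 consecutive first-dose dates, with the OLE dose at day +252 and AE onset on each of the 28 days from that dose.
- True onset on or after the dose and in the same calendar month: 94.1% are placed in the double-blind period. The exceptions are doses given on the 1st.
- True onset anywhere in the first 28 OLE days: 52.3% are placed in the double-blind period. The others are correctly placed, nearly all because they fall in the next calendar month.
- Moving the dose by 3 days either way leaves both figures unchanged to one decimal.

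**Step 5: the same test on an OLE-dose anchor without further checks.** Every pair with *a* < *d* now goes to OLE: 30 × 29/2 = 435, again 435/900 = 48.3%. On the calendar, misplacement of AEs from the first 28 OLE days falls to 0%, but 52.4% of missing-day AEs from the 28 days before the dose move to OLE.

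**Step 6: year-only dates.** Under the current rule, 96.0% of year-only AEs that truly began in the first 28 OLE days are placed in the double-blind period. Anchoring these on the OLE dose could be worse. With a first dose on 23 Mar 2022 and an OLE dose on 30 Nov 2022, 252 of the 284 days from first dose to year end (89%) are double-blind, yet every 2022 year-only AE without an earlier stop date would go to OLE.

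**The case against.** The strongest objection is Step 5: without further checks, the anchor exchanges one one-sided error for another of the same size. That stands, and it is why the anchor needs the stop-date and reporting checks. What favours the anchor is consistency. The SAP already resolves doubt towards treatment: the first-treatment month uses the dose date, and SAP 3.5.1 takes missing causality as related and missing severity as severe.

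Second, both arms of the double-blind comparison gain events, because continuing benralizumab participants are shifted too. That also stands. Only the placebo column, however, receives events under the wrong drug.

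Third, acute reactions are the events least likely to lack a start day. Dosing is normally on site with observation afterwards (Protocol 6.1.1), start dates are a collected variable (8.3.2), and SAEs are reported within 24 hours of awareness (8.3.7). This stands as a limit on the practical effect.

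Fourth, other provisions might be thought to settle the allocation. The 3.5.1 fallback does not, since on-treatment spans both periods. The ever-active rule in SAP 2.1.3 is written for erroneously treated participants; read literally, it would reclassify every placebo participant who enters the OLE. A separate OLE SAP is possible (SAP 1), but the double-blind tables are governed by this one.

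**Conclusion.** The gap is real and minor. A missing-day AE in the calendar month of the first OLE dose is always classed as double-blind unless the dose was given on the 1st. About half of such AEs would be misplaced (48.3%) if AE day and dose day are uniform over a 30-day month and stop dates do not help. How many AEs lack a start day is not stated; probably few. Safety is descriptive, and no primary or key secondary efficacy endpoint is affected.

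A reader might infer three stronger things that the documents do not support:
- **All AEs in the first four weeks on benralizumab go to placebo.** Only the calendar month of the dose is affected, and about 48% of missing-day AEs in the first 28 days are placed correctly.
- **The rule biases the comparison in favour of benralizumab.** Both columns gain events. The net effect depends on how early-OLE AEs with partial dates differ between arms, which cannot be known from the plan.
- **Events are hidden.** AEs remain in the listings, and hypersensitivity events are listed separately (SAP 4.2.9.1). They may be tabulated in the wrong period, but they are not lost.

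**What to change.** Add to SAP Appendix 8.3, for AE start dates with only the day missing and identically in both arms: if the start month is that of the first OLE dose, set the start to the date of that dose. Keep the existing rule if the stop date, or any available record that the AE was reported at or before Visit 13 pre-dose, shows an earlier onset. Use the recorded stop date for this check, because 8.3 generally imputes a missing end day to the last day of the month, which cannot show that onset was earlier. Protocol 8.3.4 asks about health problems since the previous visit, so the reporting visit will often be informative where it is recorded.

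Leave the year-only rule as it is, apart from the same two checks. Report by randomised arm the count of AEs whose period remains ambiguous, so that a reader can see whether any of this matters.

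The cost is a few sentences in the SAP and minor programming before the primary database lock. The downside is that some AEs that began shortly before the switch and were still ongoing will move to the OLE tables. That error is of similar size but in the opposite direction, which is the more cautious one for placebo switchers.
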